5.3.2.1. RSV RNA \log_{10} viral load qRT-PCR

Log₁₀ Viral Load

Descriptive statistics and mean (SE) graphs will be shown of the \log_{10} viral load actual values and changes from baseline. For exploratory purpose the \log_{10} viral load actual values and changes from baseline will also be shown by sampling method (measured in the mid-turbinate nasal swabs and endotracheal samples from intubated subjects).

Differences on RSV RNA \log_{10} viral load by qRT PCR between treatment groups and by analysis visit will be determined by using appropriate contrasts in the mixed model in which the primary endpoint is modelled. Nominal 95% confidence intervals will be used.

Peak viral load; Rate of decline

The Rate of decline of viral load over the first 24 hours will be analyzed using descriptive statistics including the geometric mean and the coefficient of variation (CV).

The log peak viral load and rate of decline of RSV RNA viral load will be compared for active groups versus placebo groups using a general linear model with treatment and strata included as fixed effects.

Residuals of the final model will be plotted in a normal probability plot.

In case the model does not fit the log peak value data well, the log transformation (ie. the log of log peak viral load) will be considered as dependent variable. The data from the model will be reported as (adjusted) differences in least squares (LS) means (in the case of untransformed data) or (adjusted) geometric mean ratios (in case of log-transformed data) of active dose groups versus placebo, including 95% confidence intervals using appropriate contrasts.

RSV viral load AUC's.

The same model used for the primary analysis will be used to test for a dose response relationship on the viral load AUC until Day 10, until Day 14 and until 1 day after last dose for subjects with treatment extension (if applicable) (respectively $AUC_{1-10Days}$, $AUC_{1-14Days}$ and $AUC_{1-xxDays}$). No corrections for multiplicity will be made, thus the significance level of alpha (α^*) will be kept at 0.05. The differences in these AUCs for active versus placebo will be derived using appropriate contrasts deriving least square mean differences, including the 95% 2 sided confidence intervals.

The sensitivity analysis will be similar as for the primary endpoint, using the calculated viral load AUCs per subject based on the trapezoidal method (AUC_{0-240h} , AUC_{0-336h} and AUC_{0-xxh}) as indicated in section 5.3.1.1.

Proportion of subjects with undetectable RSV viral load

The proportion of subjects within the RSV RNA viral load categories (undetectable, detectable and quantifiable) will be shown in a frequency tabulation per analysis time point (with corresponding 95% CI), per treatment group and per phase (treatment, follow-up and combined treatment + follow-up).

Subjects with missing data on that analysis visit will not be counted in the denominator for the proportion.

In addition, a stratified logistic regression model will be used to analyze the outcome.

Time to peak viral load

This time-to event variable will be analyzed as indicated above using Kaplan-Meier analysis.

Time to virus undetectable [time-to event]

This time-to event variable will be analyzed as indicated above using Kaplan-Meier analysis.

Additionally, the time-to event data will be analyzed using the logrank test and Gehan-Wilcoxon method.

Time to virus undetectable [interval censored]

The differences in time to RSV RNA being undetectable of active dosing regimens versus placebo treatment will also be estimated using the accelerated failure time model based on interval censored data. Treatment and stratum will be added as fixed categorical effects, while log baseline viral load will be added as a continuous fixed covariate.

Treatment effect versus placebo will be reported as an acceleration factor including 95% confidence intervals for each active treatment group. Estimated survival curves will be created based on the mean baseline viral load value and weighted average for each stratum.

The baseline \log_{10} viral load will be included as the continuous covariate. Other covariates and or baseline indicators may be included in the model when of predictive value. The model building procedure will be used.

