Vital signs	X	bid	bid	bid	bid	bid	bid	bid	bid	bid	bid

Phase Day	Screening 0	Treatment Phase			Follow-up Phase ^a							
		1	2	3 to 6 ^b	7 ^c (+2 days)	8 to 9	10 (+2days)	11 to 13	14 (+2 days)	15 to 27	28 (±2 days) EoS	
Study Procedure^d												
Nasal Swabs ^q												
Mid-turbinate nasal swab (if non-intubated) or endotracheal sample (if intubated): RSV diagnosis confirmation, viral and bacterial coinfection ^r	X											
Mid-turbinate nasal swab (if non-intubated) or mid-turbinate nasal swab and endotracheal sample (if intubated): RSV viral load, viral resistance (genome sequencing), biomarker, and infectious RSV viral load (plaque assay) ^s		X ^t	X	X	X		X		X			X
Clinical Laboratory Assessments												
Blood sampling for hematology ^u	X		X		X				X			
Blood sampling for biochemistry ^u	X				X				X			X
Urinalysis ^v	X			X					X			
Pharmacokinetics ^q												
Blood sampling for pharmacokinetics	Day 1 to Day 2											
		Post Dose 1	Post Dose 2									
		0.25 - 2h	0.5 - 1h 7h (±4)									
Group X ^w :		X	(X) ^x		X							
Group Y ^w :		X		(X) ^x	X							
Ongoing Subject Review												
Prior and Concomitant therapy	X	X	X	X	X	X	X	X	X	X	X	X
Adverse events	X	X	X	X	X	X	X	X	X	X	X	X

Abbreviations: bid: twice daily; ECG: electrocardiogram; eCOA: electronic clinical outcome assessment; eCRF: electronic case report form; EoS: end of study; IDMC: Independent Data Monitoring Committee; LD: loading dose; MD: maintenance dose; PK: pharmacokinetic(s); Q4h: every 4 hours; Q8h: every 8 hours; RSV: respiratory syncytial virus; SpO₂: peripheral capillary oxygen saturation.

Footnotes:

- a. If a subject is discontinued from study drug, a follow-up visit will be scheduled 2 days (+2 days), 5 days (+2 days), 9 days (+2 days), and 23 days (± 2 days) after the last dose of study drug was administered. Assessments should be performed as indicated in the Time and Events Schedule, respectively for the Day 7, Day 10, Day 14, and Day 28 visit.
- b. The subject may be discharged after Day 2 study procedures, but may also remain hospitalized if deemed appropriate by the investigator. Hospitalization duration will not be extended solely for study purposes.
- c. If treatment duration is increased to up to 10 days, then all assessments performed on Day 7 will again be performed 1 day (+2 days) after administration of the last MD.

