9.1.3. Double-blind Treatment Phase

Day 1 (Day of Randomization and Loading Dose)

Eligible subjects will be randomized on Day 1. Study drug administration should start as soon as possible, but no later than 4 hours after randomization. Subjects will be dosed with a single oral LD on Day 1. Depending on the time of screening/enrollment, subjects will receive the first MD of study drug on Day 1. Subjects will receive no more than 2 doses per calendar day.

Assessments to be performed on Day 1 are specified in the [Time and Events Schedule](#). The mid-turbinate nasal swab (if non-intubated) or the mid-turbinate nasal swab and endotracheal sample (if intubated) should be taken as close as possible to and before the LD on Day 1.

Day 2 to Day 5/6 (End of Treatment)

Study drug administration continues until 10 doses have been taken unless treatment duration is extended. Subjects will receive 9 MDs without regard to food intake twice daily (at least 8 hours apart and maximum 16 hours apart, with no more than 2 doses per calendar day) through Day 5/6 (depending on the timing of the LD). The date and time of dose administration, the date and time of food intake (limited to the food ingested within 30 minutes before or after study drug administration), and the type of food will be recorded in the eCRF for hospitalized subjects. The subject may be discharged after Day 2 following completion of study procedures. Subjects may

also remain hospitalized if warranted by the subject's clinical status. In case the subject is discharged prior to the completion of treatment, study drug will continue to be administered at home by the parent(s)/caregiver(s) until all doses are administered. Instructions regarding study drug administration will be given to the parent(s)/caregiver(s) by the investigator or a qualified member of the study-site personnel.

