Assessments will be performed as detailed in the [Time and Events Schedules](#). The parent(s)/caregiver(s) eCOA and the mid-turbinate nasal swabs (if non-intubated) (from the same nostril throughout the study) or endotracheal samples (if intubated) are to be taken once daily prior to study drug administration at approximately the same time each day. In case of nostril bleeding or irritation during the collection of a mid-turbinate nasal swab, all subsequent nasal swabs will be performed on the contralateral nostril. Should the study drug duration be increased to up to 10 days (following review of the data by the IDMC), samples will be taken every day up to and including 1 day (+2 days) following the last dose of study drug. Samples will be collected through Day 6 whether the subject is in hospital or has been discharged. In case mid-turbinate nasal swabs are collected at home, the subject's parent(s)/caregiver(s) should collect nasal swab specimens after being trained by the investigator/study-site personnel. Parent(s)/Caregiver(s) of subjects will be required to document the actual dates and times of collection of the nasal swab at home on the electronic device used for eCOA. Nasal swabs collected at home should be stored immediately between 2°C and 8°C (in the refrigerator) and brought to the site at the next visit.

Hospitalization duration will not be extended solely for study purposes. Telephone calls to parent(s)/caregiver(s) to facilitate compliance with study procedures between outpatient study visits are encouraged.

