9.2. Efficacy Evaluations

Viral Load Determination

As an evaluation of antiviral activity of lumicitabine, RSV viral load will be measured in mid-turbinate nasal swabs (obtained from non-intubated subjects) or in mid-turbinate nasal

swabs and endotracheal samples (obtained from intubated subjects or via suction through tracheostomy or other sampling methods) using qRT-PCR performed at the central laboratory. Samples for the determination of RSV viral load will be taken as close as possible and before the LD on Day 1 and once daily at approximately the same time each day prior to study drug administration between Day 2 and Day 6 (whether hospitalized or not), and at the Day 7, Day 10, Day 14, and Day 28 visits. For each subject, the different mid-turbinate nasal swabs should be collected from the same nostril. However, in case of nostril bleeding or irritation during the collection of a mid-turbinate nasal swab, all subsequent nasal swabs will be performed on the contralateral nostril.

Quantitative culture of RSV using plaque assay may be performed centrally at timepoints selected by the virologist.

Should the study drug duration be increased to up to 10 days (following review of the data by the IDMC), 1 mid-turbinate nasal swab (if non-intubated) or 1 mid-turbinate nasal swab and 1 endotracheal sample (if intubated) will be taken every day, at approximately the same time, up to and including 1 day (+2 days) following the last dose of study drug.

Viral L-gene Sequencing for Viral Resistance

Viral sequencing analysis will be performed by sequencing the polymerase L-gene and other regions of the RSV genome (if warranted) in samples taken before treatment (at baseline), during treatment, and posttreatment, to identify preexisting sequence polymorphisms and to characterize emerging RSV variants.

The L-gene will be sequenced pretreatment in all subjects and postbaseline in subjects not achieving viral suppression. The sequencing of postbaseline samples may be triggered at the discretion of the sponsor's virologist, based on the changes in RSV viral load observed in each individual subject and the limits of the sequencing assay and taking into account the limits of the sequencing assay. The impact of newly identified mutations on in vitro antiviral activity of lumicitabine will be assessed.

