- The relationship between viral load and duration and severity of signs and symptoms of RSV infection as assessed by the PRESORS questionnaire completed by the clinician in the eCOA device.
 - The impact of the baseline viral subtype and genotype on the antiviral activity.
 - The impact of lumicitabine on the duration and severity of signs and symptoms of RSV infection as assessed by the PRESORS questionnaire completed by the subject’s parent(s)/caregiver(s) in the eCOA device.
 - The relationship between the clinician eCOA and parent(s)/caregiver(s) eCOA responses.
 - Medical resource utilization.
 - The impact of lumicitabine on the infectious viral load using a quantitative culture of RSV (plaque assay) may be performed in a central laboratory at timepoints selected by the virologist.
 - The comparison of the RSV viral loads measured in the mid-turbinate nasal swabs and endotracheal samples from intubated subjects.

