5.3.2. Analysis Methods

Descriptive statistics

The descriptive statistics that will be shown will include the number of subjects, mean, standard deviation, standard error, 95% confidence interval, median, range and interquartile range.

Time-to event variables

All Time-to event variables will be analyzed using Kaplan-Meier estimates analysis, A summary table including number of subjects included in the analysis, number of subjects censored, 25th and 75th percentiles and median time-to event, with 95% confidence intervals based on log-log transformation method, will be presented. The data will be presented graphically using the Kaplan-Meier estimate of the survival function by treatment.

Accelerated failure time (AFT) model

When indicated time-to event variables will be compared between each active treatment group and placebo using an accelerated failure time (AFT) model. The distribution to be used will be determined based on the goodness of fit using Akaike’s information criterion and will be selected from the following parametric families: lognormal, log-logistic, or Weibull. The AFT model will include the fixed, categorical effects for treatment (with placebo as the reference) and stratification factor.

A summary of information from the final AFT model will include parameter estimates and associated standard errors, estimated accelerated failure time ratios versus placebo and associated 95% confidence intervals, and p-values. The survival curves per treatment group of the accelerated failure time model will also be shown.

Logistic regression model

A stratified logistic regression model will be used to analyze the binary outcome, with treatment group and stratification factors as fixed effect, will be used to obtain the odds ratios (95% CI) for each comparison versus placebo.

The odds ratios including 95% confidence interval of active groups versus placebo will be derived from the final model using appropriate contrasts. Exact logistic regression models will be used in case the incidence of the events is low (< 10 events).

Model building procedure

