5.3.2.2. RSV RNA \log_{10} viral load plaque assay (exploratory endpoints)

As exploratory analysis, the viral load measured using a quantitative viral culture (plaque assay) will be analyzed with descriptive statistics and mean (SE) graphs for both the actual values and changes from baseline. Additionally this analysis will be done by swab method (measured in the mid-turbinate nasal swabs and endotracheal samples from intubated subjects).

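### The nasal versus endotracheal comparison in intubated children is planned only as separate summaries by sampling method, with no within-child result

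*SAP*

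**What the plan says.** **Objective.** SAP 1.1 repeats the protocol's exploratory objective: "The comparison of the RSV viral loads measured in the mid-turbinate nasal swabs and endotracheal samples from intubated subjects".

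**Collection.** The hospitalization Time and Events Schedule has a viral-load row that asks for a nasal swab in a non-intubated child, "or mid-turbinate nasal swab and endotracheal sample (if intubated): RSV viral load". Protocol 9.2 likewise foresees, for intubated children, nasal "swabs and endotracheal samples (obtained from intubated subjects or via suction through tracheostomy or other sampling methods) using qRT-PCR performed at the central laboratory". For Day 1, Protocol 9.1.3 states that "the mid-turbinate nasal swab and endotracheal sample (if intubated) should be taken as close as possible to and before the LD". For Day 2 to Day 5/6 the same section reads differently: "the mid-turbinate nasal swabs (if non-intubated) (from the same nostril throughout the study) or endotracheal samples (if intubated) are to be taken once daily". Footnotes s and t to the schedule join the two specimens with and/or.

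**Analysis.** SAP 5.3.2.1 plans descriptive statistics and mean (SE) graphs of log10 viral load, as actual values and changes from baseline. For exploratory purposes these "will also be shown by sampling method (measured in the mid-turbinate nasal swabs and endotracheal samples from intubated subjects". SAP 5.3.2.2 says the same of the plaque assay: "Additionally this analysis will be done by swab method". SAP 5.3.2 defines the descriptive statistics as "number of subjects, mean, standard deviation, standard error, 95% confidence interval, median, range and interquartile range".

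**The concern.** The objective is a comparison, and the design foresees two specimens from one child at one visit. The natural unit of analysis is therefore the pair. The SAP describes each specimen separately and names no within-child difference, correlation, agreement measure or listing of pairs. A reader of the report would see two columns of means and have to compare them by eye, without knowing whether the sites agree in individual children.

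The SAP handles its other two-source comparison differently. In 5.4.2, clinician and caregiver scores are linked by a Spearman correlation at the assessments where both were completed. Nothing equivalent is given for the two airway specimens.

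A second problem is who contributes to each column. Endotracheal samples exist only while a child is intubated, whereas nasal swabs are scheduled up to Day 28. The SAP does not restrict the display to visits with both results, so a difference between columns could partly reflect which children are in them.

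What is at stake is whether one exploratory objective gets an interpretable answer. No confirmatory result depends on it.

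**Working it through.** The plan states no figure on this point, so there is nothing to reproduce. The check has three parts.

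**1. Can the planned statistics recover the comparison?** Take two constructed sets of five children, with log10 values at one visit.

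- Set 1: nasal 4, 5, 6, 7, 8; endotracheal 3, 4, 5, 6, 7 in the same child order.
- Set 2: the same nasal values; endotracheal 7, 6, 5, 4, 3.

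In both sets the nasal mean is 6.0, the endotracheal mean is 5.0 and each SD is 1.58. Every statistic listed in SAP 5.3.2 is therefore identical. The within-child differences (endotracheal minus nasal) are not:

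- Set 1: every difference is -1.0, so the SD of the differences is 0 and r = +1.
- Set 2: the differences are 3, 1, -1, -3, -5, with mean -1.0. Their SD is sqrt((16 + 4 + 0 + 4 + 16)/4) = 3.16, and r = -1.

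The planned display cannot tell perfect tracking from perfect reversal. With complete pairs the difference in means is the same either way; what is missing is its precision and the agreement.

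**2. How much precision could pairing add?** The documents give no between-site correlation (rho), no expected number of intubated children and no SD by site. Assumed: equal SD at both sites, one pair per child, rho from 0.3 to 0.9, and 5, 10 or 20 pairs.

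- SE of the mean difference, sites treated as independent: SD x sqrt(2/n).
- SE from pairs: SD x sqrt(2(1 - rho)/n).
- Ratio: sqrt(1 - rho), which is 0.84, 0.71, 0.55 and 0.32 at rho 0.3, 0.5, 0.7 and 0.9.

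The 95% half-widths use t with 2n - 2 degrees of freedom (unpaired) and n - 1 (paired). For n = 10 and rho 0.5: 2.101 x sqrt(2/10) = 0.94 SD unpaired, against 2.262 x sqrt(2 x 0.5/10) = 0.72 SD paired. In SD units:

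| Pairs | Unpaired | Paired, rho 0.3 | rho 0.5 | rho 0.7 | rho 0.9 |
|---|---|---|---|---|---|
| 5 | 1.46 | 1.47 | 1.24 | 0.96 | 0.56 |
| 10 | 0.94 | 0.85 | 0.72 | 0.55 | 0.32 |
| 20 | 0.64 | 0.55 | 0.47 | 0.36 | 0.21 |

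With 5 pairs and rho 0.3 the paired interval is no narrower, because the lost degrees of freedom cancel the smaller SE.

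**3. Which children are in each column?** The reference to intubated subjects in SAP 5.3.2.1 can be read in three ways.

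- Intubated at that visit: both columns hold the same children, provided both specimens were obtained.
- Ever intubated: the nasal column keeps children after extubation and the endotracheal column loses them.
- Qualifying the endotracheal samples only: the nasal column also includes children who were never intubated.

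The SAP does not say which is meant. The number of pairs is also unsettled. If Protocol 9.1.3 is read literally for Day 2 to Day 5/6, intubated children give only an endotracheal sample on those days and no pairs exist. Under the schedule and Protocol 9.2, they do.

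**The case against.** The strongest reply is that the display is descriptive and exploratory. Each column's mean and interval is valid for that column, a side-by-side table is a minimal comparison, and the subject-level data remain, so a paired summary can be added later. This stands, and it keeps the point small.

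Three stronger readings are tempting, and the documents do not support them.

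- A reader might infer that the plan loses power or distorts the false-positive rate by running an unpaired test on paired data. No two-sample test and no interval for the nasal-endotracheal difference is planned, so there is no error rate to distort. The table above describes a calculation a reader might make from the two columns.
- A reader might infer that extubation biases the comparison. That depends on which of the three readings applies. On the first, with both specimens obtained, there is no such effect, and the required subject counts would give some warning of imbalance on the others.
- A reader might infer that the display undermines the primary endpoint. That endpoint is defined on nasal swabs, and this display does not feed into it. The documents do not say that the objective is meant to validate the nasal swab.

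It is also fair to say that a repeated-measures model may not be estimable if few children are intubated. It should not be mandatory.

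**Conclusion.** The concern holds as an improvement to one exploratory analysis. The planned statistics by sampling method cannot give the within-child difference, its precision or the agreement between sites, although the schedule and Protocol 9.2 foresee pairs. The five-child example shows this without any assumption about correlation.

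The precision gain is illustrative. It rests on equal SDs, one pair per child and assumed values of rho and n, and it ranges from none (5 pairs, rho 0.3) to a half-width about a third of the unpaired one (10 or 20 pairs, rho 0.9). A mix of different children in the two columns is possible but not established. No planned test, significance level or primary result changes.

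**What to change.** In SAP 5.3.2.1, and in 5.3.2.2 if plaque-assay data exist for both specimens:

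- Restrict the comparison to intubated subject-visits with both results.
- Report the within-child log10 difference, endotracheal minus nasal, by visit: n, mean, SD and 95% CI.
- Add a paired scatterplot or agreement plot, and a listing of the pairs.
- If children contribute several pairs and numbers allow, add a model with child as a random effect. Otherwise the by-visit summaries and the listing suffice.
- If the by-method table is kept, state which children and visits each column includes.

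In the protocol, reconcile the Day 2 to Day 5/6 wording in 9.1.3 with the Time and Events Schedule (including its footnotes) and 9.2, so that it is clear whether intubated children give both specimens on those days. The nasal swab is also the specimen for the primary endpoint, so this clarification matters beyond the present table.

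The cost is a few lines of SAP text, one small table with a plot and a listing, and a protocol clarification. If the schedule is followed, no new data are needed.

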5.3.1.1. RSV RNA \log_{10} viral load (qRT-PCR)

Table 1: Calculations and Conversion Formulae

Measurement	Formula
\log_{10} viral load actual values	\log_{10} of the actual values as measured with qRT PCR
\log_{10} viral load	Change = \log_{10} viral load actual value – \log_{10} baseline value

change from baseline	
Peak viral load	Highest value of \log_{10} viral load at or after the baseline measurement. The first record in time with this highest value is selected. This can be the baseline record or an unscheduled record.
Rate of decline of viral load over the first 24 hours	Calculated as a log decline/24 hours defined as: (24-hour log viral load after first dose of study drug – log viral load at baseline) / (date/time of 24-hour viral load sample – date/time of baseline viral load) Note, the 24-hour viral load may not have been measured at exactly 24 hours following first dose, but the actual date/time associated with the 24-hour viral load will be used in computing the viral load slope. In case the 24 hour measurement is not available the slope will be calculated using the Day 3 assessment (48 hours), using the same definition. If there is no measurement in that time frame, the slope will not be calculated.
RSV viral load AUC_{0-240h} RSV viral load AUC_{0-336h} [trapezoidal method]	Idem as RSV viral load AUC_{0-144h} from 0 hours until 144 hours using the trapezoid method (sensitivity analysis), but from 0 hours until 240 hours and 336 hours respectively.
RSV viral load AUC_{0-xxh} [trapezoidal method]	Idem as RSV viral load AUC_{0-144h} using the trapezoid method, but from 0 hours until xx hours, where xx will be calculated as 24 times the number of days with treatment + 1 day.
Time to peak viral load (hours) [Time-to event]	The time from initiation of study treatment until the first time point with the peak viral load (= event). Subjects for which the peak was reached at the baseline measurement will have time 0. Subjects for whom the peak is reached at the last observed time point will be censored at that time point. Subjects for which this last assessment is the baseline assessment will be censored at time 0. (Date and time of event or censoring - date and time of first dose of study drug)/3600, rounded to one decimal.

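### The SAP asks for a geometric mean and CV of the 24-hour rate of decline, a signed quantity for which the first is undefined and the second is not interpretable

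*SAP*

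**What the plan says.** Rate of decline of viral load is a secondary endpoint (protocol 2.1.2). SAP 5.3.1.1, Table 1, introduces the variable with "Calculated as a log decline/24 hours defined as" and then gives a ratio:

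- numerator: "24-hour log viral load after first dose of study drug – log viral load at baseline"
- denominator: "date/time of 24-hour viral load sample – date/time of baseline viral load"

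The table adds that "the actual date/time associated with the 24-hour viral load will be used in computing the viral load slope". If that sample is missing, "the slope will be calculated using the Day 3 assessment (48 hours), using the same definition". No unit or conversion factor is given for the denominator.

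For reporting, SAP 5.3.2.1 states that this rate "will be analyzed using descriptive statistics including the geometric mean and the coefficient of variation (CV"). The general paragraph on descriptive statistics in SAP 5.3.2 separately commits to the usual set: count, mean with SD, SE and confidence interval, median, range and IQR. SAP 5.3.2.1 compares active groups with placebo by a general linear model with treatment and strata. The log transformation allowed there as a fallback is for log peak viral load only.

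**The concern.** A geometric mean exists only for strictly positive values. The rate as defined is negative for any child whose viral load falls, which is what an endpoint named rate of decline looks for. The SAP gives no sign reversal, back-transformation or rule for non-positive values. The programmer would therefore either report a missing statistic or make an unplanned choice about which children to include, and that choice would depend on the outcome.

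A CV divides the SD by the mean. With a negative mean it is negative, and with a mean near zero it grows without limit, so it says nothing useful about spread.

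The label promises a value per 24 hours, but the reader is not told in what unit the time difference is taken. The reported means and differences could then fail to match their label.

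**Working it through.** The documents give no numerical result, mean or SD for this endpoint, so there is no stated figure to reproduce. The check applies the definition as printed.

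**Sign.** With V0 and V24 the baseline and 24-hour log10 values and t0 and t24 their times, rate = (V24 - V0) / (t24 - t0). Taking elapsed time in days:

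- 6 to 5 log10 over 24 h: (5 - 6) / 1 = -1.0
- 6 to 6.5 log10 over 24 h: (6.5 - 6) / 1 = +0.5

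The SAP itself allows for both signs. Falls are the hypothesised effect. Rises are implied by the time-to-peak variable, which is 0 only for children who peak at baseline. SAP 5.1.2 also sets a negative PCR result to 0, and the time-to-undetectable definition in SAP 5.3.1.1 allows an ITT-i child to have a negative baseline value. Such a child can show only no change or a rise.

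**Geometric mean and CV.** Geometric mean = exp(mean of ln x) and CV = 100 × SD / mean. One normal sample of 60, the planned number per regimen, was drawn for each of six scenarios. The assumed true means were -0.3, -0.5 and -1.0 log10 per 24 h, each with SD 0.5 and 1.0.

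| Assumed mean, SD | Expected share negative | Sample mean | Geometric mean | CV |
|---|---|---|---|---|
| -0.3, 0.5 | 73% | -0.324 | undefined | -134% |
| -0.3, 1.0 | 62% | -0.336 | undefined | -301% |
| -0.5, 0.5 | 84% | -0.442 | undefined | -113% |
| -0.5, 1.0 | 69% | -0.519 | undefined | -208% |
| -1.0, 0.5 | 98% | -0.860 | undefined | -53% |
| -1.0, 1.0 | 84% | -1.129 | undefined | -87% |

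**If non-positive values are skipped.** In the third scenario only 11 of 60 values were positive, and their geometric mean was +0.19 against an arm mean of -0.44. Reversing the sign does not help: it keeps the other 49, drops the 11 rises and gives 0.45.

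**A version that can be computed.** 10^(mean log10 rate) uses every child with a rate. For a mean of -0.442 it is about 0.36, a geometric mean fold-change in viral load per 24 h.

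**Unit.** For a fall of 1 log10 over 24 h the printed formula gives:

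- seconds: -1 / 86,400 = -0.0000116
- hours: -1 / 24 = -0.0417
- days: -1 / 1 = -1.0

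Only the last agrees with the label. The time-to-event formulas in the same table divide date-time differences by 3600 to obtain hours, so raw differences there are in seconds. No such step is written for the rate. The Day 3 fallback causes no difficulty: a fall of 2 log10 over 48 h is -2 / 2 = -1.0.

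**The case against.** The strongest reply is that this concerns two extra cells in a table. SAP 5.3.2 already supplies the mean, SD, median and the rest, and the comparison between arms comes from a general linear model that uses neither the geometric mean nor the CV. That stands, and it limits the consequence.

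A reader might infer that the reported summary would describe only children whose viral load rose. The documents do not support this: nothing in the SAP says to discard non-positive values. Read literally, the statistic is simply undefined. The selected-subset result needs an unstated filtering step, and its size rests on assumed distributions.

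A reader might also infer that the CV cannot be calculated. The SAP abbreviation list defines it as the ordinary coefficient of variation, which can be computed on signed data. The fault is that it is negative or unstable here.

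Finally, a reader might infer that the rate formula is wrong by a factor of 24 or 86,400. The printed formula is exact if elapsed time is in days, so what is shown is an unstated unit. Any mismatch would be one constant factor, leaving p-values, the CV and relative differences between arms unchanged.

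**Conclusion.** The request for a geometric mean and CV of this rate is wrong as written. That follows from the SAP's own definition of the rate and needs no assumption beyond at least one child with a fall or no change. The percentages and CVs in the table illustrate the problem under assumed means and SDs and do not predict the trial's data.

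The issue is minor. The other descriptive statistics are unaffected apart from the unit to be stated. The model comparison and the primary endpoint do not depend on the geometric mean or CV. The missing denominator unit is a point for clarification, made worthwhile by the seconds-to-hours conversion used elsewhere in the same table.

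**What to change.** In SAP 5.3.2.1, delete the geometric mean and CV for the rate of decline and rely on the statistics already listed in SAP 5.3.2. If a multiplicative summary is wanted, define it as the geometric mean fold-change in viral load per 24 h, 10^(mean log10 rate), and label it so. Deletion alone would lose that summary if it was what the sponsor intended, so the sponsor should choose between the two.

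In SAP 5.3.1.1, state that elapsed time is in days, or that the result is multiplied by 24 when elapsed time is in hours.

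The cost is two short edits to the SAP, best made before programming. Data collection, sample size and error control do not change.
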